6.1.3 Follow-Up

24 (+/- 2 hours) hours after each TPE, the following will be collected:

- Any SAEs, ADRs (refer to **Section** 7.3.2 for definitions), TEs, TEEs, as well as concomitant medications.
- Blood sample(s) will be drawn for ionized calcium levels to assess for citrate toxicity. If it is impractical to obtain a blood sample for testing ionized calcium during the follow-up (e.g. an outpatient situation), this lab assessment may be skipped.

After each TPE the Investigator will provide an overall Assessment of Safety observed for each patient by indicating his or her opinion of one of the following 3 categories best describing the patient's experience with treatment while on study:

- Excellent: defined as the treatment was well tolerated by the patient,
- Moderate: defined as ADR(s) were observed, but easily resolved or not clinically significant,
- Poor: defined as ADR(s) were observed requiring significant medical intervention.

6.2 Duration of Study

6.2.1 Planned Duration for an Individual Patient

Treatment up to one week (7 days) maximum will be documented. 24 hours (+/- 2 hours) after the last TPE, the final follow-up will be performed to identify and record any SAEs, ADRs, TEs,

³ At least one blood sample should be drawn within 90 minutes after start of each TPE. All subsequent samples should also be reported in the CRF.

TEEs, as well as concomitant medications and Investigator's overall safety assessment. This visit will also be the study completion visit.

6.2.2 Planned Duration for the Study as a Whole

The study will be considered completed, when all patients have completed the last follow-up evaluation after the last TPE during study treatment period (max 1 week, 7 days).

The estimated start of this trial is 1st quarter 2015. The estimated end for this study is 4th quarter 2020.

6.2.3 Premature Termination of the Study

Both the Investigator and the Sponsor reserve the right to terminate the study at any time. Should this be necessary, the procedures will be arranged on an individual study basis after review and consultation by both parties. In terminating the study, the Sponsor and the Investigator will ensure that adequate consideration is given to the protection of the patients' interests.

Furthermore, the Investigator should promptly inform the Independent Ethics Committee (IEC)/Institutional Review Board (IRB) and provide a detailed written explanation. The pertinent regulatory authorities should be informed according to national regulations.

Should the study be prematurely terminated, all study materials (completed, partially completed and blank CRFs, etc.) must be returned to the Sponsor.

7 ASSESSMENTS AND METHODS

7.1 Background / Baseline Information

The following assessments will be performed upon enrollment:

- Physical examination (refer to **Section** 7.3.6 for definition).
- Medical history including current concomitant medications.
- Demographic data including height, body weight (BW), gender, date of birth, and race.
- Vital signs (heart rate, respiratory rate, temperature and blood pressure measurement)
- Blood group (ABO) determination.
- Safety laboratory parameters (CBC, Chem 7, and ionized calcium; refer to **Section** 7.3.5.2 for definition).
- Pregnancy testing will be performed for females of childbearing potential.

7.2 Efficacy Assessments

Due to the small sample size with different age groups efficacy will not be measured.

7.3 Safety Assessments

7.3.1 Relevant Drug Safety Information

Any of the following drug safety information shall be collected:

- Serious adverse events (SAEs)
- Adverse drug reactions (ADRs)
- Adverse events that fall into the category of TEs and TEEs (definitions and reporting requirements see **Sections 7.3.2** and **7.3.3**).
- Post-treatment related safety reports, pregnancies, drug overdose, interaction, abuse, misuse, and medication error (see **Section** 7.3.7).

Non-serious adverse events (AEs) observed during the trial will not be captured in the case report form (except for TEs, TEEs).

Post-treatment the Investigator will provide an overall Assessment of Safety observed for each patient by indicating his or her opinion of one of the following 3 categories best describing the patient's experience with treatment while on study:

- Excellent: defined as the treatment was well tolerated by the patient,
- Moderate: defined as ADR(s) were observed, but easily resolved or not clinically significant,
- Poor: Defined as ADR(s) were observed requiring significant medical intervention.

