7.3.2 Adverse Events and Adverse Drug Reactions

7.3.2.1 Definitions

Adverse event (AE): An AE is any untoward medical occurrence in a study patient receiving an IMP and which does not necessarily have a causal relationship with this treatment. An AE can therefore be any unfavorable and unintended sign (including an abnormal laboratory finding), symptom, or disease temporally associated with the use of an IMP, whether or not related to the IMP.

Adverse drug reaction (ADR): An ADR is any noxious and unintended response to a medicinal product related to any dose. The phrase "response to a medicinal product" means that a causal relationship between the medicinal product and an ADR carries at least a reasonable possibility, i.e., the relationship cannot be ruled out.

Withdrawal due to ADR: Is a patient whose treatment with a medicinal product is discontinued because of an ADR. Any such events will be followed up by the Investigator until the event is resolved or until the medical condition of the patient is stable. All follow-up information collected will be made available to the Sponsor.

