7.3.2.2 Collection

The condition of the patient will be monitored throughout the study. ADRs will be elicited using a standard non-leading question such as "How have you been since the last evaluation?" If children or adolescent patients are unable to adequately understand and respond to this question, the information will be obtained from the patient's guardian and/or Investigator or study nurse.

Any ADR or above defined AE which occurs during the study will be noted in detail on the appropriate pages of the CRF. If the patient reports several signs or symptoms, which represent a

single syndrome or diagnosis, the latter should be recorded in the CRF. The Investigator responsible will grade the severity of all ADRs/AEs (mild, moderate or severe), the seriousness (non-serious or serious) and causality, as defined below (Sections 7.3.2.3, 7.3.2.4, and 7.3.3). The Sponsor is responsible to assess the expectedness of each ADR/AE (expected or unexpected), as defined below (Section 7.3.2.4).

In the event of clinically significant abnormal laboratory findings, the tests will be repeated and followed-up until they have returned to normal and/or an adequate explanation is available.

Diseases, signs and symptoms and/or laboratory abnormalities already existing before the first administration of the medicinal product are not considered as ADRs/AEs when observed at a later stage unless they represent an exacerbation in intensity or frequency (worsening).

The Investigator responsible should always provide detailed information concerning any abnormalities and the nature of, and reasons for any necessary action(s), as well as any other observations or comments, which are useful for the interpretation and understanding of the patients' ADRs/AEs.

7.3.2.3 *Severity*

The intensity/severity of all ADRs/AEs will be graded as follows:

- mild: an ADR/AE, usually transient, which causes discomfort but does not interfere with the patient's routine activities;
- moderate: an ADR/AE which is sufficiently discomforting to interfere with the patient's routine activities;
- severe: an ADR/AE which is incapacitating and prevents the pursuit of the patient's routine activities.

Grading of an ADR/AE is up to the medical judgment of the Investigator and will be decided on a case by case basis.

7.3.2.4 *Causality*

The following causality definitions should be used for classification of each AE:

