Probable: Event or laboratory test abnormality, with reasonable time relationship to drug

intake.

Unlikely to be attributed to disease or other drugs.

Response to withdrawal clinically reasonable.

Re-challenge not required.

Possible: Event or laboratory test abnormality, with reasonable time relationship to drug

intake.

Could also be explained by disease or other drugs.

Information on drug withdrawal may be lacking or unclear.

Unlikely: Event or laboratory test abnormality does not follow a reasonable time relationship

to drug intake.

Could also be explained by the patient's clinical state or by environmental factors or other therapies administered.

Not related: Reports for which sufficient information exists to conclude that the etiology is

unrelated to the IMP.

Unclassified: Reports which for one reason or another are not yet assessable, e.g., because of outstanding information (can only be a temporary assessment).

The following causality definitions should be used for classification of each ADR:

Probable: Reports or laboratory test abnormality, with reasonable time relationship to drug

intake

Unlikely to be attributed to disease or other drugs Response to withdrawal clinically reasonable

Re-challenge not required.

Possible: Reports or laboratory test abnormality, with reasonable time relationship to drug

intake

Could also be explained by disease or other drugs

Information on drug withdrawal may be lacking or unclear.

Classification of ADRs:

ADRs will be classified by the Sponsor as either expected or unexpected:

expected: an adverse event that is listed in the current edition of the Investigator's Brochure.

• unexpected: an adverse event that is not listed in the current edition of the Investigator's Brochure, or that differs because of greater severity or greater specificity.

7.3.2.5 *Outcome*

The outcome of all reported ADRs has to be documented as follows:

- 1. recovered, resolved
- 2. recovering, resolving
- 3. not recovered, not resolved
- 4. recovered, resolved with sequelae
- 5. fatal
- 6. unknown

NOTE: A patient's **death** per se is not an event, but an outcome. The event which resulted in patient's death must be fully documented and reported, even in case the death occurs within 4 weeks after treatment with medicinal product ended, and without respect of being considered treatment-related or not.

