11.1. SAEs, ADRs, TEs, and TEEs

A Serious Adverse Event (SAE) is any untoward medical occurrence at any dose that

- results in death
- is life-threatening
- requires in-patient hospitalization or prolongation of existing hospitalization
- results in persistent or significant disability/incapacity
- is a congenital anomaly/birth defect
- is another important medical event

An Adverse Drug Reaction (ADR) in the context of this study is any noxious and unintended response to octaplas related to any dose; this means that a causal relationship between octaplas and the reported reaction cannot be ruled out, i.e. the relationship must be determined to be at least possibly related to administration of *octaplas* by the investigator or by Octapharma's medical expert or an adjudicator of the independent data monitoring committee (TEEs and TEs). Reactions with a missing or indeterminate causality assessment will also be classified as ADRs.

Serious Adverse Events (SAEs), Thrombotic events (TEs) and thromboembolic events (TEEs) will be handled in exactly the same fashion as ADRs in the context of the safety analysis. The only difference is that TEs and TEEs will be included in the analysis regardless of the causality assessment; even if such an event is reported as not related to study drug, it will be included in all data listings and tabulations. For the remainder of this section the term 'event' will thus be used to refer to any ADR, TE, or TEE.

All of the below will feature this classification (SAE, ADR, TE, TEE) as additional event characteristic if applicable.

All events for each patient, including multiple occurrences of the same reaction, will be listed in full detail, including reported term, MedDRA preferred term and system organ class, onset, duration, time to the event occurrence from last dose, causality, dosage, severity, seriousness and actions taken. The listing will include the number of the last infusion prior to each event and the relative time. An evaluation to identify any event with increased frequency over time will be performed.

For each age group and for the study as a whole the following will be given:

- Total number of events reported
- Number of events divided by the total number of TPEs

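### If Protocol 7.3.1 governs, a non-serious event that the investigator judges unrelated and not a TE/TEE need not be recorded, so the plan's second assessors cannot review it

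*Protocol*

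**What the plan says.** **What is captured.** Protocol 7.3.1 collects SAEs, ADRs and TEs/TEEs, then adds: "Non-serious adverse events (AEs) observed during the trial will not be captured in the case report form (except for TEs, TEEs"). ADRs are not named in that exception, although a bullet above it collects them. The TE/TEE bullet reads "Adverse events that fall into the category of TEs and TEEs (definitions and reporting requirements see" and then points to 7.3.2 and 7.3.3; the list of thrombotic signs is in 7.3.4.

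Protocol 7.3.2.2 has a different rule: "Any ADR or above defined AE which occurs during the study will be noted in detail on the appropriate pages of the CRF". The AE defined just above it, in 7.3.2.1, is any untoward occurrence, related or not.

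**What an ADR is.** Protocol 7.3.2.1 asks that a "causal relationship between the medicinal product and an ADR carries at least a reasonable possibility, i.e., the relationship cannot be ruled out". Section 7.3.2.4 gives AEs five causality levels: Probable, Possible, Unlikely, Not related and Unclassified (temporary only). Not related is the one level where "sufficient information exists to conclude that the etiology is" unrelated to the product. A second list opens with "The following causality definitions should be used for classification of each ADR" and has only Probable and Possible.

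**Who may overrule the investigator.** SAP 11.1 explains an ADR as a case where "the relationship must be determined to be at least possibly related to administration of" the product. That judgment may come from the investigator, or from the sponsor's "medical expert or an adjudicator of the independent data monitoring committee (TEEs and TEs"). For TEs/TEEs, Protocol 7.3.4 has three adjudicators, and Table 1 settles disagreements in favor of yes.

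**The concern.** The plan does not rely on the investigator alone. The sponsor's expert can make an event an ADR, and Adjudicators 2 and 3 can make it a TE/TEE when the investigator said no. All of them work from recorded or reported events. Under 7.3.1, the investigator's own judgments on causality and TE/TEE status help decide whether a non-serious event is recorded, so the opinion open to overruling can also keep the event from the people who could overrule it.

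Rates of SAEs, ADRs, TEs and TEEs are the primary endpoint, and there is no control group against which under-capture would show. Events lost this way can only lower the ADR and TE/TEE rates. If some sites follow the wide reading of 7.3.2.2 and others follow 7.3.1, about 10 to 15 sites could also contribute data under different rules.

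**Working it through.** The plan gives no figure to reproduce: the minimum of 40 patients is stated not to be power-based. The check compares the rules.

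**1. Which combinations reach the CRF.** Cross serious (yes/no), investigator-rated TE/TEE (yes/no) and four causality levels: 2 × 2 × 4 = 16 combinations. Unclassified is left out because it is temporary. Under 7.3.1, an event is recorded if it is serious, an ADR or a TE/TEE. The 8 serious combinations and the 4 that are non-serious but TE/TEE are recorded whatever the causality. The other 4 are non-serious and not TE/TEE:

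| Investigator's causality | 7.3.1, ADR = Probable or Possible | 7.3.1, ADR = not positively ruled out | 7.3.2.2 read as all AEs |
|---|---|---|---|
| Probable | recorded | recorded | recorded |
| Possible | recorded | recorded | recorded |
| Unlikely | not recorded | recorded | recorded |
| Not related | not recorded | not recorded | recorded |

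Under 7.3.1, 2 of 16 combinations (first reading) or 1 of 16 (second) are missed. Not related is missed on both readings. Under the wide reading of 7.3.2.2, none is missed.

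**2. Which reading of 7.3.2.2 is likelier.** The flow chart (3.2.1), the visit procedures (6.1.2, 6.1.3) and the final follow-up (6.2.1) list only SAEs, ADRs, TEs and TEEs for recording. That fits 7.3.1, but no text ranks the two sections.

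**3. Whether second assessors can reach a missed event.** Under 7.3.4, Adjudicator 2 starts once a TE/TEE is on the CRF, and the IDMC receives reported reactions and cases. The SAP 11.1 sponsor-expert step classifies reported reactions. None of these starts from an unrecorded event.

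Table 1 rows (Adjudicators 1/2/3 → database) are: yes/no/no → yes; yes/yes/no → yes; no/yes/no → yes; no/no/yes → yes; no/yes/yes → yes; yes/no/yes → yes. Three of six begin with no, and all three end yes. These rows need a record despite the investigator's no. An SAE or a recorded ADR supplies one; a non-serious event judged unrelated need not.

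**4. What 7.3.4 adds.** It lists signs and symptoms that sites would be expected to report. The investigator's TE/TEE question concerns an event already reported, so the report may come before the opinion. That narrows the gap. It does not close it, because 7.3.1 exempts TEs/TEEs rather than listed symptoms and its cross-reference misses 7.3.4.

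**5. How Unlikely is treated.** For analysis, SAP 11.1 turns the ruled-out wording into a test of at least possible, and the ADR scale stops at Possible. An event that no assessor rates at least Possible, and whose causality is neither missing nor indeterminate, is not an ADR. For site recording, only the double wording in 7.3.2.1 applies, and the table shows that its two halves give different answers.

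**6. Scale only.** One patient is 1/40 = 2.5 percentage points. Exact (Clopper-Pearson) 95% limits are:
- 0/40: 0 to 1 − 0.025^(1/40) = 8.8%.
- 1/40: lower limit 1 − 0.975^(1/40) = 0.06%; upper limit, the 97.5% point of Beta(2, 39), = 13.2%.

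On the SAP's per-TPE rate, one event is 1/(40 × 1) = 2.5 per 100 TPEs at one TPE per patient, and 1/(40 × 7) = 0.36 per 100 at seven. The range of one to seven is an assumption. These figures show how coarse the rates are; they do not estimate how many events are missed.

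**The case against.** The strongest reply is that selective capture is an openly stated choice, and every review covers only what is collected. The explicit exclusion in 7.3.1, backed by the flow chart and visit lists, makes divergent recording speculative. Sites also receive training and eCRF completion guidelines (8.1.2), which are not among the documents. Much of this stands. The choice itself is not an error, and divergence between sites is a risk, not a finding. What remains is that the plan wrote rules for overruling an investigator's no, and the capture rule limits where they can act.

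Other safeguards also continue: individual review of out-of-threshold vital signs and laboratory values (9.2.3), patient profiles for a medical expert (9.2), expert review of other significant events (SAP 11.1 footnote) and source-to-CRF monitoring (11.1). They can raise a signal, but none is the causality or TE/TEE second assessment, and monitoring checks the CRF against whichever capture rule applies.

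A reader might infer more than the documents support:
- *That Unlikely is unsettled for the ADR rates.* SAP 11.1 and the two-level ADR scale settle it; only site recording is open.
- *That Unclassified is a further gap.* It is temporary by definition, and SAP 11.1 counts missing or indeterminate causality as an ADR.
- *That adjudication is defeated.* SAEs and recorded ADRs can fill the Adjudicator 1 no rows, and the IDMC sees ADRs and unrelated SAEs quarterly.
- *That three rows of six measures impact.* It counts table rows, not events.

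**Conclusion.** The point holds in a narrow form. Sections 7.3.1 and 7.3.2.2 are not reconciled. If 7.3.1 governs, a non-serious event judged unrelated and not a TE/TEE need not be recorded, and neither the SAP 11.1 sponsor-expert route nor the Table 1 rows with Adjudicator 1 no can operate on it. Under the wide reading of 7.3.2.2, the gap disappears.

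Any bias is downward, in the ADR and TE/TEE rates. It might be inferred that the whole primary endpoint is affected, but SAEs are captured whatever their causality, so SAE rates are not biased by this route. The number of affected events is unknown and may be zero. The events most exposed are ambiguous non-serious ones; the product's known mild reactions are unlikely to be called unrelated. Severity is minor to should-fix.

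**What to change.** 1. Reconcile Protocol 7.3.1 and 7.3.2.2 into one capture rule. Name ADRs in the 7.3.1 exception and point to 7.3.4 for TEs/TEEs.
2. Require every sign or symptom on the 7.3.4 list that is new or worsened since the first infusion to be recorded, whatever the investigator's causality or TE/TEE opinion. Forward these records to Adjudicators 2 and 3, so that the Adjudicator 1 no rows can operate.
3. State, as a sponsor choice, whether non-serious events rated Unlikely are recorded for the sponsor's medical expert. They need not go to the IDMC unless a TE/TEE is suspected, since SAP 11.1 limits IDMC causality input to TEs/TEEs. Recording an event does not make it an ADR; the SAP 11.1 test still decides.
4. State in the SAP and CSR that second-assessor review covers only recorded events. If the rule changes during the study, report rates by capture rule.

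Full AE capture is not required; other non-serious events rated Not related would stay unrecorded, as the protocol chose. The cost is a protocol amendment with IEC/IRB submission, a short SAP clarification and some extra CRF lines and coding over about one week per patient, with no new visit or test. Some disease-related symptoms will be recorded and then adjudicated as not TE/TEE. A mix of capture rules in one small dataset is likely: protocol version 07 is dated October 2018 and the planned start was the first quarter of 2015, so enrollment is presumably under way.

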7.3.2 Adverse Events and Adverse Drug Reactions

7.3.2.1 Definitions

Adverse event (AE): An AE is any untoward medical occurrence in a study patient receiving an IMP and which does not necessarily have a causal relationship with this treatment. An AE can therefore be any unfavorable and unintended sign (including an abnormal laboratory finding), symptom, or disease temporally associated with the use of an IMP, whether or not related to the IMP.

Adverse drug reaction (ADR): An ADR is any noxious and unintended response to a medicinal product related to any dose. The phrase "response to a medicinal product" means that a causal relationship between the medicinal product and an ADR carries at least a reasonable possibility, i.e., the relationship cannot be ruled out.

Withdrawal due to ADR: Is a patient whose treatment with a medicinal product is discontinued because of an ADR. Any such events will be followed up by the Investigator until the event is resolved or until the medical condition of the patient is stable. All follow-up information collected will be made available to the Sponsor.

7.3.2.2 Collection

The condition of the patient will be monitored throughout the study. ADRs will be elicited using a standard non-leading question such as "How have you been since the last evaluation?" If children or adolescent patients are unable to adequately understand and respond to this question, the information will be obtained from the patient's guardian and/or Investigator or study nurse.

Any ADR or above defined AE which occurs during the study will be noted in detail on the appropriate pages of the CRF. If the patient reports several signs or symptoms, which represent a

single syndrome or diagnosis, the latter should be recorded in the CRF. The Investigator responsible will grade the severity of all ADRs/AEs (mild, moderate or severe), the seriousness (non-serious or serious) and causality, as defined below (Sections 7.3.2.3, 7.3.2.4, and 7.3.3). The Sponsor is responsible to assess the expectedness of each ADR/AE (expected or unexpected), as defined below (Section 7.3.2.4).

In the event of clinically significant abnormal laboratory findings, the tests will be repeated and followed-up until they have returned to normal and/or an adequate explanation is available.

Diseases, signs and symptoms and/or laboratory abnormalities already existing before the first administration of the medicinal product are not considered as ADRs/AEs when observed at a later stage unless they represent an exacerbation in intensity or frequency (worsening).

The Investigator responsible should always provide detailed information concerning any abnormalities and the nature of, and reasons for any necessary action(s), as well as any other observations or comments, which are useful for the interpretation and understanding of the patients' ADRs/AEs.

7.3.2.3 *Severity*

The intensity/severity of all ADRs/AEs will be graded as follows:

- mild: an ADR/AE, usually transient, which causes discomfort but does not interfere with the patient's routine activities;
- moderate: an ADR/AE which is sufficiently discomforting to interfere with the patient's routine activities;
- severe: an ADR/AE which is incapacitating and prevents the pursuit of the patient's routine activities.

Grading of an ADR/AE is up to the medical judgment of the Investigator and will be decided on a case by case basis.

7.3.2.4 *Causality*

The following causality definitions should be used for classification of each AE:

Probable: Event or laboratory test abnormality, with reasonable time relationship to drug

intake.

Unlikely to be attributed to disease or other drugs.

Response to withdrawal clinically reasonable.

Re-challenge not required.

Possible: Event or laboratory test abnormality, with reasonable time relationship to drug

intake.

Could also be explained by disease or other drugs.

Information on drug withdrawal may be lacking or unclear.

Unlikely: Event or laboratory test abnormality does not follow a reasonable time relationship

to drug intake.

Could also be explained by the patient's clinical state or by environmental factors or other therapies administered.

Not related: Reports for which sufficient information exists to conclude that the etiology is

unrelated to the IMP.

Unclassified: Reports which for one reason or another are not yet assessable, e.g., because of outstanding information (can only be a temporary assessment).

The following causality definitions should be used for classification of each ADR:

Probable: Reports or laboratory test abnormality, with reasonable time relationship to drug

intake

Unlikely to be attributed to disease or other drugs Response to withdrawal clinically reasonable

Re-challenge not required.

Possible: Reports or laboratory test abnormality, with reasonable time relationship to drug

intake

Could also be explained by disease or other drugs

Information on drug withdrawal may be lacking or unclear.

Classification of ADRs:

ADRs will be classified by the Sponsor as either expected or unexpected:

expected: an adverse event that is listed in the current edition of the Investigator's Brochure.

• unexpected: an adverse event that is not listed in the current edition of the Investigator's Brochure, or that differs because of greater severity or greater specificity.

7.3.2.5 *Outcome*

The outcome of all reported ADRs has to be documented as follows:

- 1. recovered, resolved
- 2. recovering, resolving
- 3. not recovered, not resolved
- 4. recovered, resolved with sequelae
- 5. fatal
- 6. unknown

NOTE: A patient's **death** per se is not an event, but an outcome. The event which resulted in patient's death must be fully documented and reported, even in case the death occurs within 4 weeks after treatment with medicinal product ended, and without respect of being considered treatment-related or not.

